8.1.1.7 OTHER

Refer to Protocol 1 (IMT2022-1-P1) for other materials needed to complete the study.

Refer to Protocol 2 (IMT2022-1-P2) for meal challenge in diabetic subjects.

8.1.2 DOSING AND ADMINISTRATION

The dosing of intravenous insulin and intravenous dextrose will be determined by the glucose values measured by the Dexcom G6 continuous glucose monitors, the difference between this measurement and the desired glucose range of 100-140 mg/dL, the glucose rate of change, the current weight based doses of intravenous insulin and/or dextrose that are under the control of the FUSION system, and the rules of Ideal Medical Technologies FUSION glucose control system.

8.2 PREPARATION/HANDLING/STORAGE/ACCOUNTABILITY

8.2.1 ACQUISITION AND ACCOUNTABILITY

Ideal Medical Technologies FUSION closed loop glucose control system that is to be utilized in this study will be hand delivered by a representative of Ideal Medical Technologies to the Emory University Clinical Research Center at least two weeks prior to the initiation of the study. This will allow for adequate inservicing of the principal investigator and all pertinent study personnel as to the use of the complete closed loop glucose control system. The study site will store this system in a secure location so that only study personnel who will be participating in the study will have access to it. After the study has either been completed or cancelled, all equipment supplied to the study site by Ideal Medical Technologies will be immediately returned to Ideal Medical Technologies (at Ideal Medical Technologies expense).

8.2.2 FORMULATION, APPEARANCE, PACKAGING, AND LABELING

Medical Device Labeling

The medical device under study in this Early Feasibility Study protocol will be labeled as follows:

“Ideal Medical Technologies

[name]

DEMONSTRATION OF AN ARTIFICIAL INTELLIGENCE BASED CLOSED LOOP GLUCOSE CONTROL SYSTEM AS A THERAPEUTIC MODALITY IN TYPE 1 AND TYPE 2 DIABETIC PATIENTS

Protocol IMT 2022-1

CONFIDENTIAL

Version1.0.7

22 August 2022

[name]

[name]

[contact]

Storage & Operating temperature of 41-95 F

CAUTION Investigational device. Limited by Federal (or United States) law to investigational use"

8.2.3 PRODUCT STORAGE AND STABILITY

Store and operate all components of medical device under study at room temperatures in range of 41-95 degrees Fahrenheit.

8.2.4 PREPARATION

Not applicable.

8.3 MEASURES TO MINIMIZE BIAS: RANDOMIZATION AND BLINDING

Not applicable.

8.4 STUDY INTERVENTION COMPLIANCE

Adherence to the study protocol will be determined through monitoring by Ideal Medical Technologies personnel. In addition, any deviations from the study protocol will be documented on the CRF. Ideal Medical Technologies will review the CRF forms after each study session to ensure adherence to the studies inclusion criteria, exclusion criteria, and for the presence of a signed informed consent document. Please refer to the following document for the studies monitoring plan:

001_IMT_CRC_T1DM_T2DM_Clinical Monitoring Plan

8.5 CONCOMITANT THERAPY

Not applicable.

8.5.1 RESCUE MEDICINE

The study site will supply rescue medication that will be obtained locally. The following rescue medications may be used:

1. 15 mL of 50% Dextrose for intravenous delivery (IV push), every 10 minutes as needed.
2. Glucagon (1 mg/mL) for Intramuscular or intravenous delivery. May give repeat dose 15 minutes after first dose.

The 50% dextrose and Glucagon rescue medications will be used to treat the following conditions:

- 1) Severe hypoglycemia, which is defined as a Reference Glucose Value less than 54 mg/dL.
- 2) Moderate hypoglycemia (Reference Glucose Value in the range of 54-69 mg/dL) that is accompanied by any of the following neurological signs of hypoglycemia: Anxiety, irritability, sweating, hunger, shakiness, fatigue, pale skin, lethargy, seizures.
- 3) Neuroglycopenia, which is defined as hypoglycemia of sufficient duration and degree to interfere with normal brain metabolism and function. Neuroglycopenia may occur at Reference Glucose Values greater than or equal to 70 mg/dL. If the subject has signs of hypoglycemia such as anxiety, irritability, sweating, hunger, shakiness, fatigue, pale skin, lethargy, or seizures, they will be treated with 15 mL of 50% Dextrose."

These medications will be hand pushed into the subject's intravenous line by the study nurse or given by intramuscular injection in the case of Glucagon. The date and time of rescue medication administration as well as the name and dosage regimen of the rescue medication will be recorded on the case report forms.

In addition to the above rescue medications, in cases of severe hypoglycemia, moderate hypoglycemia with hypoglycemia symptoms, or neuroglycopenia, the subjects will also be offered snacks and glucose containing juices to treat their hypoglycemia and related symptoms.

9 STUDY INTERVENTION DISCONTINUATION AND PARTICIPANT DISCONTINUATION/WITHDRAWAL

9.1 DISCONTINUATION OF STUDY INTERVENTION ON INDIVIDUAL SUBJECT

In the context of this study, termination is defined as the act of bringing either the study on one subject, or the entire study to a permanent end.

On each subject the study will be immediately terminated for any of the following reasons:

A. Termination Criteria for individual subjects:

The study will be terminated on individual subjects if any of the following criteria are met:

1. Subject or their legal authorized representative requests withdrawal from the study for any reason.
2. The clinical study nurses are unable to insert two working Dexcom G6 CGM's prior to beginning the closed loop glucose control session.
3. Subject has a Reference Glucose Value less than 54 mg/dL.
4. Subject has signs of prolonged severe hyperglycemia, as defined by Reference Glucose Value > 240 mg/dL for more than 2 hours.
5. Subject has signs of DKA, as defined by a Reference Glucose Value > 240 mg/dL and blood ketones > 1 mmol/L.
6. CGM or Reference Glucose Value remains > 300 mg/dL for more than 1 hour.
7. FUSION system has only one Dexcom G6 CGM available for use for more than 4 hours.
8. FUSION system has no Dexcom G6 CGM's available for use for more than 20 minutes.
9. There are no Reference Glucose Values for a period of time greater than 60 minutes.
10. The FUSION system experiences any unanticipated adverse device effect (UADE).
11. The subject has had more than 2% of their estimated total blood volume drawn during visit 3.
12. The FUSION system delivers more than 2000 mL (insulin and dextrose infusions) during the 24-hour closed loop glucose control session.

9.2 DISCONTINUATION OF ENTIRE STUDY

A. Termination Criteria for the entire study:

The entire study will be terminated if any of the following criteria are met:

1. Two subjects experience an episode of severe hypoglycemia (Reference Glucose Value < 54 mg/dL) during the time period the FUSION system is in use.
2. Two subjects experience an episode of severe hyperglycemia, as defined by a Reference Glucose Value > 240 mg/dL for more than 2 hours.
3. One subject experiences an episode of DKA after starting the closed loop glucose control session.
4. One subject experiences an episode of HHS after starting the closed loop glucose control session.
5. The FUSION system delivers more than 2000 mL (insulin and dextrose infusions) during the 24-hour closed loop glucose control session in two subjects.
6. The FUSION system experiences any unanticipated adverse device effect (UADE).
7. The study's principal investigator determines that the safety of the studies subjects is being compromised through use of the FUSION system.

If subjects are removed from the study due to hypoglycemia or the development of diabetic ketoacidosis, they will have ongoing monitoring and care in the CRC as noted in [Recovery Period](#) (pages 107-108). If a subject signs an informed consent but does not receive closed loop glucose control, they may be replaced. If a subject begins the closed loop glucose control portion of the study, they may not be replaced.

If the study has been terminated on only one subject for a reason other than an unanticipated adverse device effect, the study may continue. If the entire study has been terminated, it may not be resumed until the study's sponsor has submitted study results to the FDA, the study sponsor has presented plans to mitigate the risks that led to the study's termination, and the FDA has approved resumption of the study.

9.3 PARTICIPANT DISCONTINUATION/WITHDRAWAL FROM THE STUDY

Participants are free to withdraw from participation in the study at any time upon request.

The reason for subject withdrawal or involuntary removal from the study will be recorded on the CRF. If subjects withdraw themselves from the study after starting the closed loop glucose control session, they will be discharged from the CRC after meeting all of the discharge criteria noted in [Recovery_Period](#) on page 106. If a subject signs an informed consent but does not receive closed-loop glucose control, they may be replaced. If a subject begins the closed loop glucose control portion of the study, they may not be replaced.

As the study is limited to 32 hours of glucose control/monitoring, no long term follow up will be done for the subjects who either complete the study, or for those who are withdrawn for any reason, except as required to record and monitor any adverse events or unanticipated problems.

9.4 LOST TO FOLLOW-UP

Not applicable.

10 STUDY ASSESSMENTS AND PROCEDURES

10.1 EFFICACY ASSESSMENTS

The following procedures/evaluations will be performed on the subjects:

1. Review of medical history and inclusion/exclusion criteria to determine eligibility for the study. This may be performed by any qualified study personnel.
2. Obtain informed consent. This may be performed by any qualified study personnel.
3. Draw blood for creatinine, alanine aminotransferase, hemoglobin, HbA1c, and C-peptide. These labs will be analyzed in the hospital's central laboratory. For women of childbearing age of 18-55 years inclusive, obtain a urine pregnancy test. Blood draw will be performed by any qualified personnel. If these results have already been obtained as part of the subject's routine laboratory studies, the already obtained results may be used to assess the subject for inclusion/exclusion criteria.
4. For subjects who have signed an informed consent and whose lab results do not exclude them from the study, an appointment for visit 3 will be set. This appointment must occur within 2 weeks of the date the informed consent was signed.
5. During visit 3, the subject will undergo closed loop control of their blood glucose level from time 5 to 29 hours utilizing Ideal Medical Technologies FUSION closed loop glucose control system. Refer to the SOP for set up, initiation and use of this system. To initialize the glucose control software the study RN will enter the patient's weight (Kg), study identification number, and initial Reference Glucose Value. The glucose control range of 100-140 mg/dL will be automatically defaulted to by the glucose control software. On initiation of the closed loop glucose control session the study RN will obtain a blood sample for glucose analysis from the arterialized retrograde intravenous line every 30 minutes. This blood sample will be immediately analyzed for a Reference Glucose Value on the Nova StatStrip Hospital Glucose Meter System. Results from this test will be entered into the appropriate case report form as soon as it becomes available. The frequency of checking Reference Glucose Values is outlined in the study protocol on pages 102-103. The study RN will be responsible for making sure the insulin and dextrose syringes in the syringe pumps being used for glucose control remain at least 20% full (at least 10 mL volume remaining in 50 mL BD syringe) throughout the course of the closed loop glucose control study.
6. A total of approximately 60 blood draws for glucose analysis will be obtained during the study. The blood volume removed with each blood draw will be 0.5 mL, for a total blood loss of no more than 40 mL's. This is in addition to the 10 mL removed previously for lab analysis to verify eligibility for the study. The total volume of blood removed from the subject for purposes of completing this study should be less than 80 mL's over a period of 2 weeks.
7. At the conclusion of the study the two Dexcom G6 CGM's and the two intravenous lines will be removed from the subject by the study clinical nurse. The subjects will be discharged from the CRC when they have met the discharge criteria noted in the study protocol (IMT2022-1-P2).

The subjects who have participated in the study will be given the following information after conclusion of the study:

1. Their average glucose value over the period of closed loop glucose control.
2. Their CV value over the period of closed loop glucose control.
3. Their percent time in range < 70 mg/dL over the period of closed loop glucose control.
4. Their percent time in range 70-180 mg/dL over the period of closed loop glucose control.
5. Their percent time in range > 180 mg/dL over the period of closed loop glucose control.

10.2 SAFETY AND OTHER ASSESSMENTS

10.2.1 SAFETY

The exclusion criteria which are used to screen for potential subjects eliminates those with hepatic failure, signs of significant hepatic disease as defined by an alanine aminotransferase greater than three times the upper limit of normal, any signs of renal failure, subjects with any history of congestive heart failure, subjects with a history of ischemic heart disease/cerebrovascular accident/seizures and eliminates all females who are pregnant. The purpose of these exclusion criteria is to avoid first in human trials on subjects with severe organ compromise, and exposure of a fetus to an untested medical device.

Independently monitoring Reference Glucose Values every 10-60 minutes will ensure subject safety should they experience hypoglycemia that the closed loop glucose control system is either unaware of or is unable to effectively treat. This monitoring will allow for early intervention in case the subjects experience severe hypoglycemia (Reference Glucose Value < 54 mg/dL) or moderate hypoglycemia (Reference Glucose Value 54-69 mg/dL) with clinical signs of hypoglycemia.

10.2.2 PHYSICAL EXAM/LABS

The visit 1 physical exam will be limited to recording the subject's weight. No vital signs will be recorded. During the closed loop glucose control portion of the study the subject's vital signs will be monitored with a frequency of at least every 1 hour.

No EKG's will be needed for purposes of completing this study. No radiologic studies will be needed for purposes of completing this study.

The screening labs which are part of the exclusion criteria will be performed in the central laboratory. The blood for these labs will be stored as per institution specific guidelines as the study itself does not require that the blood used for these studies be stored for any length of time. The overall blood volume needed for purposes of completing the study is estimated to be approximately 50 mL but may be as much as 80 mL.

10.2.3 SPECIAL ASSAYS

The Reference Glucose Values to be done at the bedside will be performed on a Nova StatStrip Hospital Glucose Meter System. The study personnel will require specialized training on use of the Nova StatStrip Hospital Glucose Meter System, if they have not previously been trained on its use.

10.2.4 USE OF EXISTING MEDICAL RECORD DATA

For purposes of performing the screening criteria the existing medical records available at the time of the subject's routine visit to the adult endocrinology clinic will be used whenever possible. In addition to medical history and physical exam information, this may also include use of necessary lab work to include creatinine, alanine aminotransferase, hemoglobin, HbA1c, C-peptide, and urine pregnancy test.

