1.2 SCHEMA

[figure not shown]
Visit 1:
Screening

Total N = 500: Screen potential participants by inclusion and exclusion criteria.
Schedule eligible participants for Visit 2 = Enrollment

Visit 2:
Enrollment
Time -2
Weeks to
-1 Week
Prior to CRC
Study

[figure not shown]
[figure not shown]
Total N = 16: Screen potential participants by inclusion and exclusion criteria; obtain informed consent. Obtain history, document. Perform baseline assessments. Record height and weight (Kg). Obtain blood work to include: 1) creatinine, 2) alanine aminotransferase (ALT), 3) hemoglobin, 4) hemoglobin A1C, 5) C-peptide. For female subjects within age range of 18-55 obtain urine pregnancy test. For subjects whose labs do not exclude them from the study, proceed to Visit 3

Visit 3 must occur no later than 2 weeks from Visit 2

Visit 3:
Time 0 to
31 hours

Total N = 8: Administer initial study intervention of placement of two Dexcom G6 CGM's in the abdominal position on arrival to the CRC. Place two peripheral IV lines for study intervention. Once the two Dexcom G6 CGM's begin to return glucose values to the Dexcom Receivers, and the subjects begin to consume their first study meal, commence the 24-hour closed loop glucose control session. The first study meal will be lunch, which will be served at 12 PM

DEMONSTRATION OF AN ARTIFICIAL INTELLIGENCE BASED CLOSED LOOP GLUCOSE CONTROL SYSTEM AS A THERAPEUTIC MODALITY IN TYPE 1 AND TYPE 2 DIABETIC PATIENTS

Protocol IMT 2022-1

CONFIDENTIAL

Version1.0.7

22 August 2022

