7.2 EXCLUSION CRITERIA

- A. Subjects will be excluded from the study if they meet any of the following criteria:
 1. Have participated in an interventional medical, surgical, or pharmaceutical study within 30 days of screening.
 2. Have a known hypersensitivity to any of the components of study treatment.
 3. Have skin disease/injury at Dexcom G6 CGM insertion site(s) that would prevent insertion of the CGM.
 4. Currently abuses drugs or alcohol or has a history of abuse that in the investigator's opinion would cause the individual to be noncompliant.
 5. Have a medical condition that in the opinion of the investigator could affect study participation and/or personal well-being.
 6. Have a clinically significant history or presence of any of the following conditions:
 - a. Hepatic failure or has alanine aminotransferase (ALT) greater than 3 times the upper limit of normal.
 - b. Has an estimated GFR <60 ml/min/1.73 m² or End Stage Kidney Disease on renal replacement therapy.
 - c. Type 2 diabetic subjects who have a C-peptide level less than 0.2 nmol/L (these subjects will be referred to their primary care doctor or endocrinologist for further work up).
 - d. Have congestive heart failure of class 1 or greater on the NYHA classification system.
 - e. Have a history of seizures.
 - f. Have a history of cerebrovascular accident.

DEMONSTRATION OF AN ARTIFICIAL INTELLIGENCE BASED CLOSED LOOP GLUCOSE CONTROL SYSTEM AS A THERAPEUTIC MODALITY IN TYPE 1 AND TYPE 2 DIABETIC PATIENTS

Protocol IMT 2022-1

CONFIDENTIAL

Version1.0.7

22 August 2022

- g. Have a history of ischemic heart disease.
- 7. For female subjects of potential childbearing age (age 18 to 55) they will be excluded if:
 - a. Pregnant.
 - b. Refuse to agree to a pregnancy test at the time of enrollment.
 - c. Have a positive urine pregnancy test at the time of enrollment.
- 8. Have a positive COVID-19 test within 14 days of visit 3.
- 9. Have any COVID-19 related symptoms in the 14-day period prior to visit 3.
- 10. Have a known unprotected COVID-19 exposure in the 14-day period prior to visit 3.

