7.5 STRATEGIES FOR RECRUITMENT AND RETENTION

Participants with type1 and type 2 diabetes will be recruited from the Diabetes Center at Grady Hospital and adult endocrinology clinics at Emory Healthcare, located in Atlanta, Georgia. All adult type 1 and type 2 diabetic patients being cared for in these clinics will be screened for inclusion in the study. The original screening will include age, weight, length of diagnosis of diabetes, use of insulin in the home setting, and their most recent HbA1c level. Potential subjects who pass these criteria will then be assessed for exclusion criteria. Potential subjects who pass the exclusion criteria will be approached for participation in the study. Willing participants will be scheduled for enrollment during visit 2. Subjects

who sign an informed consent during visit 2 will have blood drawn to evaluate their hemoglobin, HbA1c, ALT, creatinine, and C-peptide (type 2 diabetic subjects) levels. Female subjects aged 18-55 inclusive who have signed an informed consent will also have a urine pregnancy test performed during visit 2. It is anticipated that 500 adult type 1 and type 2 diabetic subjects will need to be screened to yield 8 subjects for participation in the study. It is expected that the inclusion criteria will eliminate 97% of potential enrollees. It is expected that the exclusion criteria will eliminate another 30% of the remaining potential enrollees. Study participants will be compensated for participation in the study.

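### Sections 10.1 item 3 and 10.2.4 let an already obtained urine pregnancy test, with no stated maximum age, count for eligibility, while sections 7.2, 7.5, the schema and the Schedule of Activities call for a test at enrollment

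*Combined protocol and SAP*

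**What the plan says.** **Text that ties the test to enrollment.** Section 7.2 item 7 gives three grounds for excluding women aged 18-55. Item 7a is pregnancy itself. Item 7b is declining to be tested when enrolling. Item 7c reads "Have a positive urine pregnancy test at the time of enrollment". Section 7.5 says that women in this age range who have signed consent "will also have a urine pregnancy test performed during visit 2". The schema lists the test under visit 2: "For female subjects within age range of 18-55 obtain urine pregnancy test". The Schedule of Activities has one pregnancy test, in the visit 2 column, and none at visit 3.

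**Text that allows an earlier result.** Section 10.1 item 3 lists the enrollment blood tests and adds: "For women of childbearing age of 18-55 years inclusive, obtain a urine pregnancy test". The same item ends by saying that, where results exist from routine laboratory work, "the already obtained results may be used to assess the subject for inclusion/exclusion criteria". Section 10.2.4 deals with records available at the routine endocrinology clinic visit and says "this may also include use of necessary lab work to include creatinine, alanine aminotransferase, hemoglobin, HbA1c, C-peptide, and urine pregnancy test". Neither section gives a time window.

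**Stated purpose.** Section 10.2.1 says the exclusions eliminate pregnant women, and that one aim is to avoid "exposure of a fetus to an untested medical device".

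**The concern.** One set of sections makes the enrollment test mandatory. The other allows an existing result to stand in for it. A site that follows the second set is still following the protocol, so whether a woman has a current test depends on which section the staff apply.

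At stake is the safeguard itself. Only one pregnancy test is scheduled. If an earlier negative replaces it, no scheduled step before the device is started would detect a pregnancy that began after that earlier test. Exclusions 7b and 7c would also have nothing to act on: with no test offered at enrollment there is no refusal to record and no enrollment result to read.

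**Working it through.** No sample size, power or event count is involved. The check is to set every place that governs pregnancy testing side by side and follow the timing.

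| Place | What it does | Timing of the test |
|---|---|---|
| 1.2 Schema | Orders the test | Visit 2 |
| 1.3 Schedule of Activities | One test marked | Visit 2 only |
| 7.2 items 7b, 7c | Excludes on refusal or a positive result | Enrollment |
| 7.5 | States that the test is performed | Visit 2, after consent |
| 10.1 item 3 | Orders the test, then allows existing results for eligibility | No window |
| 10.2.4 | Names the test among usable record results | No window |
| 7.2 item 7a | Excludes pregnancy | Not tied to a test |
| 10.3.9 | Excludes a consented woman found pregnant before treatment | Any time before treatment; schedules no test |

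**Step 1: does the permission reach the pregnancy test?** In 10.1 item 3 the test is ordered in the same list item as the reuse sentence, and nothing exempts it. Section 10.2.4 counts it as laboratory work and names it. Read together, they cover it.

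**Step 2: does the permission reach eligibility, or only chart pre-screening?** Section 10.2.4 on its own could be limited to visit 1. Section 10.1 item 3 cannot: it allows existing results for assessing the inclusion and exclusion criteria, in the item that sets out the enrollment tests. The conflict therefore rests mainly on 10.1 item 3, with 10.2.4 in support.

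**Step 3: how old can the result be at treatment?**

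- *Test done at visit 2.* The schema and section 8.1.1.3 require visit 3 within 2 weeks of visit 2, and section 10.1 item 4 sets the same limit from the date of consent. The result is at most about 2 weeks old.
- *Existing result reused.* Its age at visit 3 is its age at visit 2 plus up to 2 weeks. The documents put no limit on the first term, so they put none on the sum.

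**Step 4: is there a later check?** The Schedule of Activities shows no pregnancy test at visit 3, and the visit 3 screening in section 8.1.1.4 covers glucose, ketones and acute symptoms only. Items 7a and 10.3.9 remain, but both depend on the pregnancy being known or coming to light in some other way.

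**Step 5: who is affected?** Only a woman aged 18-55 who already has a negative result on record, and only if the site reuses it. The study treats eight subjects and the documents do not give the number of women, so the count lies between 0 and 8.

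**The case against.** The strongest reply is that the specific, mandatory text governs. Section 7.2 holds the eligibility criteria, 7b and 7c both speak of enrollment, and an older result does not answer a question about a test at enrollment. Section 7.5, the schema and the schedule agree. Section 10.1 item 3 is only permissive, is confined to results from routine laboratory work, and has a sentence about the blood draw between the pregnancy test and the reuse permission, so it might be meant for the blood tests alone. Section 10.2.4 opens by limiting itself to screening from clinic records.

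Much of this stands. A careful site could read the protocol that way and test everyone at visit 2, and 10.2.4 alone would not establish the conflict. But the reply needs the reader to decide which section prevails, and the protocol does not say. Because 10.2.4 expressly names the urine pregnancy test, it is hard to hold that 10.1 item 3 excludes it.

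A reader might go further and infer that undated results are acceptable, that every woman aged 18-55 is affected, or that the protection in 10.2.1 is defeated. The documents do not support these readings. They omit a maximum age but do not say that results may lack a date. A woman with no earlier test on record is unaffected. Items 7a and 10.3.9 still exclude a pregnancy that is known or found.

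A reader might also extend the point to hemoglobin, HbA1c, creatinine, ALT and C-peptide, which fall under the same reuse wording. For these, the lack of a maximum age is unspecified detail, no harm from reuse is shown, and no change is asked for here.

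**Conclusion.** The inconsistency is real and lies in current protocol text. Section 10.1 item 3, supported by 10.2.4, permits what 7.2 items 7b and 7c, 7.5, the schema and the Schedule of Activities do not provide for. As written, a woman with an earlier negative result could reach device exposure without a current test. The protection is weakened, not removed.

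In size, the oldest possible result at treatment goes from about 2 weeks to no stated limit, for some number of women between 0 and 8. Treating a pregnant subject is a possibility, not an expected outcome. No endpoint, analysis or sample size is affected. The point is worth correcting because it concerns the only scheduled pregnancy check and the remedy costs almost nothing.

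The conclusion assumes that the reuse sentence in 10.1 item 3 covers the whole item, including the pregnancy test. If the sponsor meant only the blood tests, the wording should say so, and the same edit achieves that.

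**What to change.** Reconcile the sections in favor of the protocol's own visit 2 test:

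1. In section 10.1 item 3, state that the permission to use existing results does not apply to the urine pregnancy test, which is performed at visit 2.
2. In section 10.2.4, remove the urine pregnancy test from the list of record results that may be used.

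Sections 7.2, 7.5, the schema and the Schedule of Activities then need no change. The result would be at most about 2 weeks old at treatment. The edit narrows the interval but does not close it, since the visit 2 test may still precede visit 3 by up to 2 weeks.

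The cost is two wording changes in an amendment. No visit or procedure is added, because the test is already scheduled at visit 2; at most, one urine test is done that might otherwise have been skipped for each woman concerned.
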